1.3 Schedule of Activities (SoA)

The schedule of activities during the study is summarised for all participants in [Table 1](#), except the PK/PD subset of 12 participants which is summarised in [Table 2](#).

If the Coronavirus Disease 2019 (COVID-19) pandemic prevents participants from coming to the site, participants can have their study visit assessments performed remotely as judged appropriate by the investigator. This must be discussed with the sponsor before being implemented. In such a case, the investigator will perform a telemedicine visit and will make every effort, where applicable, to contact the participant's general practitioner or specialist physician to ensure all important medical information and safety event(s) occurring since the last visit are collected. Guidance on how to collect protocol-planned assessments will be provided to the investigator in a separate document. Such document will be filed in the trial master file. Independent ethics committees (IECs)/institutional review boards (IRBs) will be notified of the changes as applicable locally. Of note, as the adapted visit deviates from the regular protocol plan, the changes will be recorded as protocol deviations related to COVID-19.

Table 1 Schedule of Activities for All Participants Except the Pharmacokinetic/Pharmacodynamic Subset

Procedure	Screening		Intervention Period						EoS/EW
	End of Week	Day	Week 4	Week 8	Week 12	Week 16	Week 20	Week 24	
Visit Window	-	-	±3 days	±3 days	±3 days	±3 days	±3 days	±3 days	
Informed consent	X								
Eligibility	X	X							
Demography	X								
Medical and surgical history	X								
Physical examination [f]	X	X [a]			X				X
MRI scan [g]	X								
Disease-specific medical history	X								
Prior disease-specific treatment	X								
Body weight	X								X
Vital signs	X	X [a]	X	X	X	X	X	X	
12-lead electrocardiogram[b]	X		X						X
ECOG Score	X								
Injection triptorelin 6M		X							
Blood samples for triptorelin PK		X [a]	X	X	X	X	X	X	
Blood sample for testosterone PD [h]	X	X [a, e]	X	X	X	X	X	X	
Blood samples for PSA [h]	X	X [a, e]			X				X
Blood samples [c] laboratory safety tests	X	X [a, e]							X
Local tolerance [d]		X							
Previous (excluding disease-specific) and concomitant medication	X	X	X	X	X	X	X	X	
Adverse events	X	X	X	X	X	X	X	X	

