6M=6-month formulation, AE=adverse event, ALT=alanine aminotransaminase, AST=aspartate aminotransaminase, CRF=case report form, D=day; ECG=electrocardiography; ECOG=Eastern Cooperative Oncology Group, EoS/EW=end of study/early withdrawal, Hb=haemoglobin, M1b=distant metastasis bone(s), MRI=magnetic resonance imaging; PD=pharmacodynamic, PK=pharmacokinetics, PSA=prostate-specific antigen, WBC=white blood cell.

-
- a Assessment or blood sampling to be performed prior to study intervention injection. PK Predose sampling window (\leq 30 minutes).
 - b ECG to be assessed as clinically indicated at any other time in the study as required.
 - c Haematology (WBC, platelet count, Hb), Blood Chemistry (creatinine, glucose, ALT, AST, alkaline phosphatase, bilirubin (total and conjugated)) will be tested at the local laboratory. Glucose: fasting levels in all participants at Screening visit, fasting levels on Days 1 and 169. Fasting is not necessary for diabetic participants.
 - d Injection site to be specifically checked 2 hours \pm 15 minutes after injection for local reactions on Day 1. After Day 1, any local reaction AE to be collected on the CRF in the same manner as other AEs.
 - e Measurement of testosterone, PSA and laboratory safety tests for analysis purposes only and not for eligibility. The screening testosterone, PSA and safety laboratory test results will be used for eligibility.
 - f Complete physical examination to be performed (or brief physical examination based on investigator judgement). Participants, particularly those with M1b status, should be advised regarding clinical signs suggestive of spinal cord compression.
 - g Scan for prostate gland or the whole body, only if necessary, based on investigator's judgement. An MRI scan is not required if performed within 1 month of screening.
 - h Testosterone and PSA testing will be performed at the central laboratory.

See Appendix [10.5](#) for ECOG performance scale.

Table 2 Schedule of Assessments for the Pharmacokinetic/Pharmacodynamic Subset of Participants

Procedures	Screening	Intervention Period												EoS/EW
		-	-	-	-	-	-	-	Week 4	Week 8	Week 12	Week 16	Week 20	
End of Week	-	-	-	-	-	-	-	-						
Day	D-28 to D-1	D1	D2	D3	D5	D8	D15	D22	D29	D57	D85	D113	D141	D169
Visit Window										±3 days				
Previous (excluding disease-specific) and concomitant medication	X	X	X	X	X	X	X	X	X	X	X	X	X	X
Adverse events	X	X	X	X	X	X	X	X	X	X	X	X	X	X

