6M=6-month formulation, AE=adverse event, ALT=alanine aminotransaminase, AST=aspartate aminotransaminase, CRF=case report form, D=day; ECG=electrocardiography; ECOG=Eastern Cooperative Oncology Group, EoS/EW=end of study/early withdrawal; h=hours; Hb=haemoglobin, M1b=distant metastasis bone(s); MRI=magnetic resonance imaging; PD=pharmacodynamic, PK=pharmacokinetics, PSA=prostate-specific antigen, WBC=white blood cell.

a Assessment or blood sampling to be performed prior to study intervention injection.

b ECG to be assessed as clinically indicated at any other time in the study as required.

c Sampling on Day 1. PK time sampling windows:

- Pre-dose (≤ 30 mins) prior to study drug injection
- 1h, 2h, 3h post-dose ± 5 mins
- 4h, 6h, 8h post-dose ± 15 mins
- 12h post-dose ± 30 mins
- 24h post-dose ± 1 hour
- 48h post-dose ± 2 hours
- 96h post-dose ± 3 hours
- 168h post-dose ± 4 hours
- Day 15 (2 weeks post-dose) ± 24 hours
- Day 22 (3 weeks post-dose) ± 24 hours
- Day 29, 57, 85, 113, 141, 169 = clinic visit time windows (± 3 days)

d Haematology (WBC, platelet count, Hb), Blood Chemistry (creatinine, glucose, ALT, AST, alkaline phosphatase, bilirubin (total and conjugated) will be tested at the local laboratory.

Glucose: Fasting levels in all participants at Screening visit, fasting levels on Days 1 and 169. Fasting is not necessary for diabetic participants.

e Injection site to be specifically checked 2 hours ± 15 minutes after injection for local reactions on Day 1. After Day 1 any local reaction AEs to be collected on the CRF in the same manner as other AEs.

f Measurement of testosterone, PSA and laboratory safety tests for analysis purposes only and not for eligibility. The screening testosterone, PSA and safety laboratory test results will be used for eligibility.

g Complete physical examination to be performed (or brief physical examination based on investigator judgement). Participants, particularly those with M1b status, should be advised regarding clinical signs suggestive of spinal cord compression.

h Scan for prostate gland or the whole body, only if necessary, based on investigator's judgement. An MRI scan is not required if performed within 1 month of screening.

i Testosterone and PSA testing will be performed at the central laboratory.

See Appendix 10.5 for ECOG performance scale.

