8.4.1 Time Period and Frequency for Collecting AE and SAE Information

All AEs and SAEs will be collected from the signing of the ICF until the EoS at the time points specified in the SoA (Section 1.3).

Medical occurrences that begin before the start of study intervention but after obtaining informed consent will be recorded on the AE section of the case report form.

All SAEs will be recorded and reported to the sponsor or designee immediately and under no circumstance should this exceed 24 hours of awareness of the event, as indicated in Appendix 10.3. The investigator will submit any updated SAE data to the sponsor within 24 hours of it being available.

Investigators are not obligated to actively seek information on AEs or SAEs after conclusion of the study participation. However, if the investigator learns of any SAE, including a death, at any time after a participant has been discharged from the study, and he/she considers the event to be reasonably related to the study intervention or study participation, the investigator must promptly notify the sponsor.

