9.4.5 Safety Analyses

Safety endpoints are indicated in Section 3.

All safety data will be included in the participant data listings. Analyses and summary tables will be based upon the safety set.

All AEs will be coded according to the Medical Dictionary for Regulatory Activities (MedDRA) version 24.1 (or higher if available) and will be classified by MedDRA preferred term and system organ class. Adverse event listings will be presented by participant, system organ class and PT.

The incidence of all TEAEs and SAEs will be tabulated overall. In addition, summary tables will be presented by maximum intensity and drug relationship.

A TEAE is defined as any AE that occurs during the active phase of the study (from study intervention injection to 24 weeks after injection) if it was not present prior to receiving study intervention, or:

- it was present prior to receiving IMP but the intensity increased during the active phase of the study.
- It became serious during the active phase of the study
- It was present prior to receiving the study intervention and the intensity was the same, but the causality changed to 'related to treatment' during the active phase of the study.

All TEAEs will be flagged in the AEs listings.

Haematological and biochemical toxicities will be recorded and graded according to the NCI CTCAE criteria, where available. The National Cancer Institute-Common Toxicity Criteria for Adverse Events (NCI-CTCAE) Grade 3 and 4 haematology and biochemistry variables by participant and by cycle will be listed.

Actual values and changes from baseline in clinical laboratory tests, physical examinations, vital signs and 12-lead ECG will be summarized using descriptive statistics at each visit. For laboratory data, abnormal values will be flagged in the data listings and a list of clinically significant abnormal values will be presented. Shift tables using the worst on-treatment grade will be presented for the number and percentage of participants with NCI-CTCAE grades.

AEs reported by investigators using the NCI-CTCAE classification (Version 5.0 or higher) will be coded using MedDRA Version 24.1 (or higher if available).

Summary incidence tables will be provided, classified by SOC, PT and associated NCI/CTC worst grade. In the event of multiple occurrences of the same AEs being reported by the same participant, the maximum intensity (Grade 5 >Grade 4 >Grade 3 >Grade 2 >Grade 1 >missing >not applicable) will be chosen.

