5.1 General Considerations

All statistical analyses will be performed using the Statistical Analysis System® software version 9.4 (or higher if available).

5.1.1 *Outputs Presentation*

5.1.1.1 *Tables Header*

Depending on the type of data, the summary tables will be presented as follows:

- For disposition, demographic and baseline data: by treatment group,
- For efficacy and safety data: by treatment group.

5.1.1.2 *Presentation of Treatment Group*

Tables, Figures and Listings (TFLs) will be displayed using the following treatment group label:
Triptorelin 6M

5.1.1.3 *Presentation of Visits / Timepoints*

Summaries by visit will be presented using visit number as collected in the Electronic Case Report Form (eCRF).

Visits in the TFLs will be presented as follows and in the following order:

Long Visit Name	Short Name
Screening	Scr
Baseline	Bsl
Day 1	D1
Day 2	D2
Day 3	D3
Day 5	D5
Day 8	D8
Day 15	D15
Day 22	D22
Week 4 Day 29	W4D29
Week 8 Day57	W8D57
Week 12 Day85	W12D85
Week 16 Day113	W16D113
Week 20 Day141	W20D141
End of Study/Early Withdrawal	EoS/EW

In the event a participant is enrolled, but does not receive study intervention, the participant will not remain in the study and EoS/EW assessment will not be performed.

5.1.2 *Descriptive Statistics*

All raw and derived variables will be listed and described using summary statistics. For categorical variables, summary statistics will be displayed using descriptive statistics by frequency count and percentages by category. The missing category will be presented if there is at least one missing category for at least one treatment group. Except otherwise specified, participants with missing data will be included in the calculation of percentages. For quantitative variables, summary statistics will be displayed using descriptive statistics by number of observations, mean, standard deviation (SD), median, minimum and maximum. Frequency and proportion of missing data will be displayed.

5.1.3 *Baseline Value*

Unless otherwise specified, baseline is defined as the last non-missing measurement taken prior to first Investigational Medicinal Product (IMP) administration (including unscheduled assessments).

5.1.4 *Reference Start Date and Study Day*

Reference start date is defined as the day of the first IMP administration.

The day of the first IMP administration will be Day 1. Study day will be calculated as:

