5.7.1.3 Statistical/analytical issues

Adjustments for Covariates

This is a single-arm study, and no statistical comparisons will be performed, so covariates adjustment is not required.

Interim Analyses and Data Monitoring

Please refer to section 3.

Multicentre Studies

This is a multicentre study conducted in China.

Multiple Comparisons/Multiplicity

No multiple testing will be performed in this study because this is a single-arm descriptive safety and efficacy study.

Active-Control Studies Intended to Show Equivalence (if applicable)

Not applicable.

5.7.2 *Analysis of Primary Efficacy Endpoint*

5.7.2.1 *Endpoint, Treatment Effect and Estimand Definition*

The co-primary endpoints of efficacy are

- To determine the percentage of participants achieving castrate levels of serum testosterone (<50 ng/dL or 1.735 nmol/L) on Day 29 ± 3 days (Week 4) and
- To determine the percentage of participants maintaining the castrate levels of serum testosterone (<50 ng/dL or 1.735 nmol/L) from Week 8 (Day 57 ± 3 days) to Week 24 (Day 169 ± 3 days).

Percentage of participants achieving castrate levels of serum testosterone on Day 29

The percentage of participants achieving castrate levels of serum testosterone on Day 29 will be obtained as the number of participants achieving castrate levels on Day 29, divided by the number of participants in the FAS. The formula is

$$\text{Percentage} = \frac{\text{Number of participants achieving castrate levels on Day 29}}{\text{Number of participants in the analysis set}} \times 100$$

Percentage of participants maintaining castrate levels from Week 8 to Week 24

Percentage of participants maintaining castrate levels of serum testosterone from Week 8 to Week 24 for the FAS will be calculated as the number of participants achieving castrate levels of serum testosterone at all visits from Week 8 to Week 24, divided by the number of assessable participants in the analysis set. The formula is

$$\text{Percentage} = \frac{\text{Number of participants maintaining castrate levels from Week 8 to Week 24}}{\text{Number of assessable participants in the analysis set}} \times 100$$

To derive the percentage of participants maintaining castration levels of testosterone, missing data between Week 8 and Week 24 will be handled as follows:

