5.8 Safety

5.8.1 *General Consideration*

All safety summaries and analyses will be based upon the Safety Set. All safety data will be included in participant data listings (see listing detail conventions in Appendix A4). This is a single-arm study, and there will be no statistical comparison between the treatment groups for safety data.

Haematological and biochemical toxicities will be recorded and graded according to the National Cancer Institute-Common Toxicity Criteria for Adverse Events (NCI-CTCAE) version 5.0 or higher, where available (refer to appendix A5 for grading using NCI-CTCAE 5.0). The NCI-CTCAE Grade 3 and 4 haematology and biochemistry variables by participant and by visit will be listed.

5.8.2 *Extent of Exposure*

Summary of the actual dose and duration of exposure will be provided on the Safety Set. Actual dose will be calculated as planned dose (22.5 mg) multiplied by (1 - percentage of residual in syringe). The definition of the duration of exposure is from first IMP administration to the date of end of study. Participant's exposure data will be listed on the Safety Set.

5.8.3 *Adverse Event*

All adverse events (AEs) recorded in the eCRF will be coded using the latest version of MedDRA dictionary in effect within IPSEN at the time of the database lock. AEs will be classified as Treatment-Emergent AEs (TEAEs) according to the rules below:

- Events with start date on or after the date of IMP administration and up to 24 weeks after date of first dose of treatment.
- Events whose severity (measured by National Cancer Institute – Common Toxicity Criteria (NCI-CTCAE) Version 5.0 grading) worsens on or after the date of IMP administration,

Refer to appendix ‘

[Partial/Missing Date Convention](#)’ for handling of partial date.

In the case where it is not possible to define an AE as treatment emergent or not, the AE will be classified by the most conservative case; i.e. treatment emergent.

In addition, if severity of an AE changes during the study, a separate AE will be recorded for each severity on the AE eCRF. The “first” and subsequent AEs will be identified based on the AE start date or the severity change date. If “first” AE record occurs before dosing, and subsequent AEs occur on or after dosing, subsequent AEs whose severity worsens compared with the severity of “first” AE record will be classified as TEAE. If “first” AE record occurs on or after dosing, “first” AE record and subsequent AEs will be classified as TEAE.

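### New adverse events with a start date on Days 170 to 172 are collected but not counted as treatment-emergent, although the Week 24 visit may validly fall on those days (minor)

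*SAP*

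**What the plan says.** **End of the treatment-emergent period.** For new events, SAP 5.8.3 requires a start date on or after dosing and "up to 24 weeks after date of first dose of treatment". Protocol 9.4.5 defines the active phase as running "from study intervention injection to 24 weeks after injection".

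**Study-day count.** SAP 5.1.4: "The day of the first IMP administration will be Day 1".

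**Final visit.** SAP 5.7.2.1 places the end of the maintenance endpoint at "Week 24 (Day 169 ± 3 days" either side. The protocol gives the same tolerance in Table 1 and in Table 2 footnote c: "Day 29, 57, 85, 113, 141, 169 = clinic visit time windows (± 3 days".

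**What is done at that visit.** In Protocol Table 1, the row "Blood samples [c] laboratory safety tests" is marked at screening, on Day 1 and at EoS/EW. The Day 1 mark carries footnote a: "Assessment or blood sampling to be performed prior to study intervention injection". ECG is marked at screening, Week 4 and EoS/EW. Physical examination is marked at screening, Day 1 before dosing, Week 12 and EoS/EW.

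**What becomes an AE, and until when.** Protocol 8.3 requires clinically significant laboratory, ECG, vital-sign and examination findings to be recorded as AEs. Protocol 8.4.1: "All AEs and SAEs will be collected from the signing of the ICF until the EoS".

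**Other rules in SAP 5.8.3.**
- Events whose severity worsens on or after dosing are TEAEs; no end date is given. Protocol 9.4.5 confines worsening to the active phase. SAP 2.6 does not list this difference.
- In the paragraph on AEs whose severity changes, an event first recorded on or after dosing is classed as a TEAE, again with no end date.
- An event whose status cannot be determined is classed as treatment-emergent.

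**The concern.** The TEAE period closes on the nominal date of the last visit, but that visit may take place up to three days later. AE collection, and the SAP 5.8.2 duration of exposure, both run on to the end of study. A compliant late visit can therefore produce an AE that is in the database, was found at a planned Week 24 assessment, and is still not treatment-emergent.

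This matters most for laboratory AEs. Under Table 1 the final visit is the only scheduled post-dose draw, so no earlier planned sample could have picked up the finding inside the period. ECG and physical examination are exposed in the same way, but each has one earlier scheduled post-dose assessment.

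Incidence of TEAEs throughout the study, up to Week 24, is a secondary endpoint. Whether an end-of-study finding enters it should not depend on which permitted day the visit was booked. The error can only lower the count.

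**Working it through.** **Step 1. Reproduce the plan's Week 24 date.**
24 weeks × 7 = 168 days after injection. SAP 5.1.4 adds one day for events on or after the reference date: 168 + 1 = Day 169. This matches the Day 169 visit in both documents. Reading the limit as inclusive, Day 169 is the last day on which a new event can be a TEAE.

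**Step 2. Compare with the visit window.**
Allowed visit days: 169 − 3 = 166 to 169 + 3 = 172, which is seven days. Days after the cut-off: 170, 171 and 172. Share of permitted days: 3/7 = 43%.

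**Step 3. Apply the SAP 5.8.3 rules to fully dated events.**

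| Event | Rule that applies | TEAE? |
|---|---|---|
| New, start Day 168 | First bullet | Yes |
| New, start Day 171, severity unchanged | First bullet fails; no other rule clearly applies | No |
| Present before dosing, worsens on Day 171 | Worsening bullet, no end date | Yes in the SAP; no under Protocol 9.4.5 |
| Found on Day 171, onset on or before Day 169 | First bullet, by start date | Yes |

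The fallback for events that cannot be classified does not help in row 2, because a full start date allows classification.

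Appendix A2 gives a related oddity. Its example dose date is 2002-08-11, so Day 169 is 2003-01-26. A new AE dated 2003-01-28 (Day 171) is not a TEAE. If the day were missing, Table 1 of that appendix would impute 2003-01-01, and the event would count.

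**Step 4. Where a new Day 171 event still appears.**
- SAP 5.8.3: the any-AE row of the overview; the SAE tables not restricted to treatment-emergent events, if serious; and the AE listing with its emergence flag.
- SAP 5.8.4 to 5.8.7: the underlying values or interpretations, in the by-visit summaries and shift tables that apply to each assessment.

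It is absent from the TEAE tables. For a non-serious event, those are the only tables by system organ class and preferred term.

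**Step 5. Illustrate the size.**
The documents give neither the share of late visits nor the rate of new findings at the final visit, so both are assumptions. Completers are taken as 165, the number in the sample-size section (195 × 0.85 = 165.75). Each AE is assumed to carry the date of the visit or sample.

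Events not counted = 165 × finding rate × share of visits on Days 170 to 172.

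| Finding rate | Share late | Events not counted | Rate as tabulated |
|---|---|---|---|
| 2% | 10% | 165 × 0.02 × 0.10 = 0.3 | 1.8% |
| 5% | 10% | 165 × 0.05 × 0.10 = 0.8 | 4.5% |
| 5% | 3/7 (even spread) | 165 × 0.05 × 3/7 = 3.5 | 2.9% |
| 10% | 60% | 165 × 0.10 × 0.60 = 9.9 | 4.0% |

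Rate as tabulated = finding rate × (1 − share late). It refers to these final-visit findings only, not to overall TEAE incidence.

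**Step 6. Check the fix.**
If the period ends at the later of Day 169 and the visit date, none of the seven permitted visit days lies outside it.

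**The case against.** **The fixed cut-off is deliberate and consistent.** Protocol and SAP agree on 24 weeks for new events. That matches the 168-day release period in Protocol 2.2 and the Week 24 endpoint. This stands as a rationale for a 24-week period, but it does not explain why a compliant Week 24 visit should fall partly outside it.

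**The SAP may already catch these events.** The sentence on an event first recorded on or after dosing has no end date. Read as covering every AE, it would make a new Day 171 event a TEAE. The more natural reading limits it to AEs whose severity changes, which is the subject of its paragraph. On the wider reading it contradicts the first bullet, so the text needs reconciling either way.

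**Stronger readings that the documents do not support.**
- A reader might infer that everything first found at a late visit is dropped. The rule turns on start date, not on detection: a sign or symptom found on Day 171 with onset by Day 169 is still a TEAE. That a laboratory AE takes the sample date is usual but is not stated.
- A reader might infer that all the missed events leave the treatment-related and grade 3+ TEAE tables too. Only events that are themselves related or of grade 3 or higher can do so. The documents give no basis for those fractions, and the loss from those tables could be zero.
- A reader might infer that the safety information is lost. It is not; step 4 lists where it remains.
- A reader might take 43% as the expected share of late visits. It is a share of permitted days and equals a share of visits only under an even spread.

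**The stakes are low.** The study is single-arm and descriptive, with no safety testing. Only new-onset events on three days are affected, and the primary endpoints are untouched. This stands and sets the severity.

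**Conclusion.** The point holds, at minor severity. By the documents' own dates, a new AE with a recorded start on Days 170 to 172 is collected but is not a TEAE under the first bullet of SAP 5.8.3 or under Protocol 9.4.5. The SAP also treats a worsening event on Day 171 differently from a new one, and differently from the protocol.

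The consequence is a one-directional undercount in TEAE outputs. With the central assumptions (5% finding rate, 10% to 43% of visits late) it is about 1 to 4 events in 165 completers; over the wider range in the working it runs from well under 1 to about 10. The date arithmetic needs no assumption. The size rests on the timing of visits, the finding rate and the dating of laboratory AEs, none of which the documents give.

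One limit on the evidence: the laboratory row of Table 2 is not in the text available for review. The statement about the only post-dose draw therefore rests on Table 1, which covers all but the 12 PK/PD participants, and on the laboratory endpoint, which is set at Week 24 alone.

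**What to change.** 1. In SAP 5.8.3 and Protocol 9.4.5, end the treatment-emergent period at the later of 24 weeks after injection and the date of the participant's Week 24/EoS visit, inclusive.
2. Apply the same end to the worsening-severity bullet in SAP 5.8.3. In the protocol, worsening is already tied to the active phase, so it follows from step 1.
3. Align the SAP sentence on events first recorded on or after dosing with that end, so that it cannot be read as an open-ended rule.
4. If the protocol is not amended, list the difference in SAP 2.6.

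The cost is about one sentence in each document, the alignment edits, and one line of programming. No visit, sample or data field is added. The one downside is that TEAE counts may rise slightly.

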The AE summaries include the following summaries:

- An overview table summarizing the
 - number and percentage of participants with at least one of the following AEs: any AE; any TEAE; any severe TEAE (CTCAE grade ≥ 3); treatment-related TEAE; TEAE leading to discontinuation from the study, Serious Adverse Event (SAE), treatment emergent SAE, treatment-related SAE, treatment emergent SAE leading to death, treatment-related SAE leading to death, treatment emergent SAE leading to discontinuation from the study, most frequent TEAEs ($>5\%$), death,
 - corresponding number of events for each of the AE categories listed above
- A summary of the number and percentage of participants reporting a TEAE by treatment group, SOC and PT,
- A summary of the number and percentage of participants reporting a TEAE by treatment group and PT,
- A summary of the number and percentage of participants reporting a TEAE by treatment group, maximum CTCAE grade, SOC and PT,
- A summary of the number and percentage of participants reporting a TEAE by treatment group, maximum causality, SOC and PT,
- A summary of the number and percentage of participants reporting a treatment-related TEAE by treatment group, maximum CTCAE grade, SOC and PT,
- A summary of the number and percentage of participants reporting a most frequent TEAE ($>5\%$) by treatment group and PT,
- A summary of the number and percentage of participants reporting a non-serious TEAE by treatment group, SOC and PT.

AEs summaries will be ordered in term of decreasing frequency for SOC and PT within SOC in the treatment group, and then alphabetically for SOC and PT within SOC if ties. AEs summaries by PT will be ordered in term of decreasing frequency of PT in the treatment group and then alphabetically for PT if ties.

AEs will be counted as follows:

- Participants with more than one AE within a particular SOC are counted only once for that SOC. Similarly, participants with more than one AE within a particular PT are counted only once for that PT;
- Participants reporting a TEAE more than once within that SOC/ PT, the TEAE with the worst-case grade (grade order: 5>4>3>2>1>missing) will be used in the corresponding grade summaries;

- Participants reporting a TEAE more than once within that SOC/ PT, the TEAE with the worst-case relationship to study medication (order: related > not related > missing) will be used in the corresponding relationship summaries;

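### SAP 5.8.3 lets grade changes add to the TEAE event counts, and judges worsening of pre-dose AEs against the wrong record

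*SAP*

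**What the plan says.** SAP 5.8.3 sets the recording rule: "if severity of an AE changes during the study, a separate AE will be recorded for each severity on the AE eCRF". It covers any change, upward or downward.

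Two classification rules follow, depending on when the AE began.

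- Onset on or after dosing: "If “first” AE record occurs on or after dosing, “first” AE record and subsequent AEs will be classified as TEAE". There is no condition on direction.
- Onset before dosing: "subsequent AEs whose severity worsens compared with the severity of “first” AE record will be classified as TEAE". The comparator is the first record of that AE.

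The overview table in the same section gives, beside participant counts, the "corresponding number of events for each of the AE categories listed above".

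The counting rules further down work per participant: "Participants with more than one AE within a particular SOC are counted only once for that SOC", with the same rule for PT, and for repeated TEAEs "the TEAE with the worst-case grade (grade order: 5>4>3>2>1>missing) will be used in the corresponding grade summaries". Protocol 9.4.5 is also about intensity within a participant: "In the event of multiple occurrences of the same AEs being reported by the same participant, the maximum intensity" is the one chosen. None of these says how events are to be counted.

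**The concern.** An AE that eases is the same episode at a lower grade. Protocol 10.3.1 treats the exacerbation of an existing condition as an AE when its frequency or intensity rises; it has no matching provision for improvement. Under SAP 5.8.3 the easing still creates a record, the record is a TEAE if onset was post-dose, and nothing stops it entering the event count. The column would then partly measure how often sites updated a grade. The severity mix can shift too: an episode going 3, 2, 1 shows as one severe TEAE among three, when it is one of one.

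The comparator for pre-dose onset is a separate defect in the same paragraph. Treatment emergence should turn on change from the state at injection. The first record may be an older grade that had already changed before the injection. This part bears on whether a participant has a TEAE at all, and so on the incidence endpoint in Protocol Section 3.

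**Working it through.** The documents state no expected number of events, so there is no planned figure to reproduce. The check applies the SAP 5.8.3 rules to constructed grade sequences, which are illustrations and not trial data.

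**Event counts**

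Let *N* be the number of records for one episode and *T* the number that are TEAEs.

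- First record post-dose: *T* = *N*.
- First record pre-dose at grade *g*: *T* = number of post-dose records with grade above *g*.

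| Onset | Grade sequence | AE records | TEAE records | Participants with a TEAE | TEAE episodes if collapsed |
|---|---|---|---|---|---|
| Post-dose | 2 throughout | 1 | 1 | 1 | 1 |
| Post-dose | 2, 1 | 2 | 2 | 1 | 1 |
| Post-dose | 1, 2, 3, 2, 1 | 5 | 5 | 1 | 1 |
| Pre-dose | pre 2; post 1 | 2 | 0 | 0 | 0 |
| Pre-dose | pre 1; post 2, 1 | 3 | 1 | 1 | 1 |
| Pre-dose | pre 1; post 3, 2, 1 | 4 | 2 | 1 | 1 |

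In the last row the post-dose Grade 2 record is a TEAE although it is an improvement from Grade 3, because it is still above the first record.

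The table assumes a new record at each change. If the recording rule means one record per distinct grade, the third row has 3 records instead of 5. The second row stays at 2, so an improvement alone still adds a TEAE.

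With a share *q* of post-dose episodes changing grade *m* times each, records per episode average 1 + *q* × *m*. The documents give neither *q* nor *m*. The result cannot fall below 1, so any effect is upward.

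The participant column is never above 1. The once-per-SOC/PT and worst-grade rules therefore contain the effect everywhere except in the number of events.

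**Comparator for pre-dose onset**

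The second TEAE bullet in SAP 5.8.3 covers events whose CTCAE grade worsens from the day of injection. Protocol 9.4.5 covers events already present whose intensity rose in the active phase. Set against the first-record rule:

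| Grades before injection | Grade after | First-record rule | SAP bullet and Protocol 9.4.5, on severity |
|---|---|---|---|
| 1, then 3 | 2 | 2 > 1: TEAE | 2 < 3, improved: not a TEAE |
| 3, then 1 | 2 | 2 < 3: not flagged | 2 > 1, worsened: TEAE |

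The two tests disagree in both rows. SAP 2.6, which lists departures from the protocol's statistical section, does not mention this one. If the Safety Set equals the planned 195 and the AE is the participant's only candidate TEAE, each such case moves TEAE incidence by 1/195 = 0.5 percentage points.

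**The case against.** The strongest reply is that the SAP never says one record is one event. Its table shells are a separate document (SAP Section 1) that was not available for this review, and a merging rule could be there. That stands as a limit: record counting is inferred from the instruction to record a separate AE and from the absence of any merging rule in the protocol or SAP. The SAP should still state the rule.

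It is also fair that the reach is narrow. The study has one arm and no safety comparison, its endpoint is TEAE incidence, and the by-term, grade and causality summaries count participants. No conclusion in the plan rests on the event column.

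On the comparator, the paragraph opens as an addition to the bullets, and SAP 5.8.3 sends undecidable cases to treatment emergent. The sequence 3, 1, then 2 after dosing might therefore be caught by the bullet. So its exclusion is not established; what is established is that two rules in one section disagree. This reply does not help with 1, 3, then 2 after dosing, where the first-record rule positively flags an improvement. Two grades must be recorded before dosing, within a screening period of up to 28 days, so these cases should be rare.

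Four stronger readings are tempting, and the documents do not support them.

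- *Every severity record is a TEAE.* This is true only for post-dose onset. With pre-dose onset, a record at or below the first grade is not a TEAE under this rule, though nothing keeps it out of the any-AE event count.
- *An SAE that eases is counted twice.* Protocol 10.3.3 separates seriousness from severity, and nothing says whether the eased record keeps the serious flag.
- *Counts are overstated by 10% to 60%.* That follows from assuming that 10% of episodes change once (1 + 0.1 × 1 = 1.1) up to 30% changing twice (1 + 0.3 × 2 = 1.6). Neither input has an anchor in the documents.
- *Counts cannot be compared with other studies or reconciled with the safety database.* The documents describe neither other studies' counting nor the database structure.

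**Conclusion.** The point holds in two limited parts. First, for AEs with onset on or after dosing, SAP 5.8.3 makes a TEAE of every severity record, improvements included, and nothing in the protocol or SAP merges them before events are counted. The number-of-events column is inflated if the plan is followed as written. The direction is upward and the size cannot be estimated. A reader might infer that TEAE incidence is inflated in the same way; it is not, because participant-level tables are protected by their own counting rules. This part assumes that the shells contain no merging rule.

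Second, the first-record comparator for pre-dose AEs conflicts with the SAP's second TEAE bullet and with Protocol 9.4.5. It can change a participant's TEAE status, but rarely.

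Neither part touches the primary endpoints. Both are worth correcting before database lock because a stated rule gives a wrong or ambiguous result and the correction is cheap.

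**What to change.** Make two changes in SAP 5.8.3.

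1. State that every number-of-events entry counts each linked episode once, at its worst post-dose grade, and that the separate severity segments are kept for listings only. For the any-AE row, an episode that ended before dosing also counts once. Carry the same rule into the table shells.
2. In the sentence on AEs whose first record precedes dosing, replace the first AE record as comparator by the last severity recorded before IMP administration. This brings the paragraph into line with the second TEAE bullet and Protocol 9.4.5.

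The cost is SAP wording and one variable linking the records of an episode. The SAP already requires first and subsequent records to be identified from start and severity-change dates, so some linkage is presupposed. If the eCRF holds it, no new data are needed.
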